Test Group III, (regardless of risk) – First 3-months postoperation, Coumadin at an INR target of 2.5 to 3.5 with 81 mg/day (75 mg/day in Italy) aspirin will be used. After 3-months, Coumadin dose will be reduced to an INR target of 2.0 to 2.5 with 81 mg/day (75 mg/day in Italy) of aspirin continued.

Control Group – Postoperatively Coumadin with an INR target on 2.5 to 3.5 with 81 mg/day (75 mg/day in Italy) aspirin throughout the study.

D. Sample Size

A sample size estimate was conducted based on FDA OPC criteria^[1]. The study is expected to test the safety of low dose (LD) therapy for anticoagulant therapy in On-X valve patients with LD therapy consisting of the use of Coumadin in combination with aspirin or the use of antiplatelet therapy alone. This study is designed as a non-inferiority study requiring only that LD therapy is not inferior to standard

Coumadin/aspirin treatment. Testing the superiority of LD therapy with adverse event rates as low as expected would require exposure of a prohibitively large patient group. It was necessary for the sample size calculation to assume an acceptable event rate for the primary endpoints of thromboembolism, thrombosis and bleeding events derived by summing the FDA OPC's. The incident rate of the sum of these three events needs to be at least as low as the OPC sum, 7.3%. Table 1 gives the resulting sample size requirements based on a variety of outcomes.

The number of patients to be enrolled in the clinical trial is based first on the ability to show that linearized adverse event rates for the primary endpoints in the test groups are not inferior to the corresponding control groups and second on the ability to show that all valve related adverse event rates in the test groups do not equal or exceed 2 times the rates determined to be acceptable for mechanical valves.

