For the first criterion above, the test group will need to have less than 6%/ptyr cumulative rate of the three events for the study to reach significance with a randomized patient population of between 150 and 250 per group followed for between 5 and 6.7 years at a statistical power of 80% with type I error of 0.05 and a maximum allowable difference between groups of 1.5%. It is expected that each of 50 centers will be able to enroll an average of 30 patients into the study balanced to provide adequate population in each sub-group, providing sufficient patient-years to test the hypothesis, which under the above conditions is around 1000 as shown in Table 1. Thus the study has 200 patients per group in AVR high risk with an average of 5 years of follow-up, or alternatively 150 patients in AVR low risk averaging 6.7 years of follow-up and and up to 250 MVR averaging 4 years of follow-up, providing the approximately 1000 patient-years per group estimated to meet hypothesis.

For the second criterion above, the established rates are the objective performance criteria (OPC) given in the FDA guidance document ⁽¹⁾. The adverse event rates for which OPCs are established include the primary endpoints of thrombosis, thromboembolism and bleeding and the secondary endpoints of paravalvular leak and endocarditis as listed below:

% per valve year (R_A)
0.8
3.0
3.5
1.5
1.2
1.2

In the comparison to OPCs for each adverse event, the null hypothesis being tested is that the true adverse event rate for each test group is equal to or greater than twice the acceptable rate. Rejecting the null hypothesis would conclude that the rate for the test groups is less than two times the acceptable rate. The null and alternative hypotheses can be written as:

Null hypothesis:	$R \ge 2R_A$
Alternative hypothesis:	$R < 2R_A$

Table 1

Sample Size Estimation for On-X Trial LD Therapy vs. Control

The sample size estimation is based on one-sided proportion test, which tests that the incidence rate of thrombosis, thromboembolism and hemorrhage in the LD therapy groups are at least as low as the control groups.

				Maximum Allowable	
Type I Error	Statistical	Expected	Expected	Difference	Needed
(One-sided	Power	Proportion	Proportion	between Two Groups	Patient
Test)		In Control	In Low Dose	to Declare Non-inferiority	Years
		Group	Group		
0.05	80%	7.3%	4.5%	2.0%	309
			5.0%	2.0%	398
			6.0%	2.0%	719
			7.3%	2.0%	2112
			4.5%	1.5%	381
			5.0%	1.5%	504
			6.0%	1.5%	992
			7.3%	1.5%	3739

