All complications should be recorded by the investigator on CRF4. Start and stop dates and etiology should be noted. The investigator will attempt to evaluate the relationship of all deaths, reoperations, explants, or cardiovascular complications to the study valve as presented in the AATS/STS guidelines ⁽²⁾ and will provide pertinent details of the event on CRF4. Copies of autopsy report and/or death summary must be included where applicable.

The investigator will report any serious or unexpected complication occurring during the investigation to the monitor within 24 hours, followed by a written report in ten working days, after the investigator first learns of the event. A serious or unexpected complication would include those complications not expected, or those occurring at a greater rate than expected when compared to the review requirements of this study (see section III F).

Adverse events are defined by the United States FDA as complications, meaning:

"Operative mortality, morbid events, and consequences of morbid events. Complications may or may not be device related."

This study uses the term "complication" to mean any adverse event or adverse device effect (a device-related adverse event), which may be mild, moderate, or severe. If as a result of a complication during a clinical investigation a subject has to be hospitalized, if hospitalization is unduly prolonged because of potential disability, if hospitalization is unduly prolonged because of potential danger to life, if a reoperative intervention has been necessary, or if the event is terminal, the complication is regarded as severe.

The definitions which appear in the following sections will be used to report complications associated with the use of the On-X prosthesis. Complications will be recorded and dated when they are observed or estimated to have occurred and treatment(s) documented. An event will be recorded once unless there are multiple occurrences of that event. For example, a cerebrovascular accident (CVA) reported once with sequelae still present at subsequent follow-visits will not be reported again. If another CVA occurs that is unrelated to the initial episode, then it is reported as a separate incident.

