4. SAMPLE SIZE CONSIDERATIONS

The study is expected to test the safety of low dose (LD) therapy for anticoagulant therapy in On-X valve patients with LD therapy consisting of the use of Coumadin® in combination with aspirin or the use of antiplatelet therapy alone. The sample size for this study was designed as a non-inferiority study requiring only that LD therapy is not inferior to standard Coumadin®/aspirin treatment. It was necessary for the sample size calculation to assume an acceptable event rate for the primary endpoints of thromboembolism, thrombosis and bleeding events derived by summing the FDA OPC's. The incident rate of the sum of these three events needs to be at least as low as the OPC sum, 7.3%.

The test group will need to have less than 6%/ptyr cumulative rate of the three events for the study to reach significance with a patient population of 200 per group followed for 5 years at a statistical power of 80% with type I error of 0.05 and a maximum allowable difference between groups of 1.5%.

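### Table 1 sizes a comparison of linearized rates with a proportion test; for a rate difference, 1000 patient-years per group give at most about 78% power at the planning rates, not 80%

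*Protocol*

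**What the plan says.** Protocol II.D makes the first basis for enrolment the ability to show that "linearized adverse event rates for the primary endpoints in the test groups are not inferior to the corresponding control groups". The planning values are:

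- **Control rate.** The three OPCs are summed: "The incident rate of the sum of these three events needs to be at least as low as the OPC sum, 7.3"% per patient-year.
- **Test rate.** II.D says "the test group will need to have less than 6%/ptyr cumulative rate of the three events".
- **Operating characteristics.** The design is set "at a statistical power of 80% with type I error of 0.05 and a maximum allowable difference between groups of 1.5"%.
- **Exposure.** The arms are described as "providing the approximately 1000 patient-years per group estimated to meet hypothesis".

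Table 1 supplies the exposure figure. Its note reads "The sample size estimation is based on one-sided proportion test", its input columns are headed as proportions, and its output is in patient-years. The row for 6.0%, margin 1.5% and one-sided 0.05 gives 992.

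On repeat events, Protocol III.C (Complication Reporting) says: "An event will be recorded once unless there are multiple occurrences of that event". A second, unrelated stroke, for example, is reported as a separate incident.

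SAP 4 repeats the power statement for 200 patients per group, "followed for 5 years at a statistical power of 80% with type I error of 0.05", with the same margin and the same 6% per patient-year.

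**The concern.** A proportion test gives each unit the variance p(1−p), because a unit either has the event or does not. A linearized rate is events divided by patient-years. Its variance is λ/T, where λ is the rate and T the exposure. A patient-year is not a yes/no trial: it can hold more than one event, and the protocol records repeat occurrences separately. Using p(1−p) in place of λ drops a factor of about 1/(1−p). At rates of 6 to 7% per patient-year, this makes the required exposure several per cent too low.

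What is at stake is the accuracy of the 80% power figure in both documents. The planned exposure of about 1000 patient-years sits almost exactly on the 992 from Table 1, so there is no reserve to absorb the difference.

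**Working it through.** **Inputs (Protocol II.D and Table 1).** Control 0.073 and test 0.060 events per patient-year, margin 0.015, one-sided α 0.05, power 80%, equal exposure per group. The distance to the margin is d = 0.015 + 0.073 − 0.060 = 0.028. The normal quantiles are 1.6449 and 0.8416.

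**Formula.** The score (Farrington-Manning) form is n = [1.6449·√V0 + 0.8416·√V1]² / d². V1 is the summed variance per patient-year at the planning rates. V0 is the same quantity at the maximum-likelihood rates restricted to test = control + 0.015.

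**Step 1: reproduce the plan's figure.** Binomial variance:

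- V1 = 0.073×0.927 + 0.060×0.940 = 0.12407
- Restricted proportions 0.06043 and 0.07543, so V0 = 0.12653
- n = (0.58508 + 0.29645)² / 0.000784 = 991.2, rounded up to **992**

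The same formula, rounded up, reproduces all 24 entries of Table 1.

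**Step 2: change only the variance.** Poisson variance:

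- V1 = 0.073 + 0.060 = 0.13300
- Restricted rates 0.06054 and 0.07554, so V0 = 0.13609
- n = (0.60678 + 0.30693)² / 0.000784 = 1064.9, rounded up to **1065** (1065/992 = 1.073)

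The simpler Wald form gives (1.6449 + 0.8416)² × 0.133 / 0.000784 = 1048.8, so **1049**. That is 5.7% above the printed 992. Against its own binomial counterpart, 979, it is 7.1% higher.

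**Step 3: power at the planned exposure.** Score form: power = Φ[(d√n − 1.6449·√V0)/√V1]. At n = 1000 this is Φ[(0.88544 − 0.60678)/0.36469] = Φ(0.764) = **77.8%**.

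| Patient-years per group | Binomial score | Poisson score | Poisson Wald |
|---|---|---|---|
| 992 | 80.0% | 77.5% | 78.0% |
| 1000 | 80.3% | 77.8% | 78.3% |
| 1005 | 80.5% | 77.9% | 78.5% |

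Exact enumeration of the Poisson score test gives 78.1% at 1000. Simulation of the Wald test (2 million runs) gives 78.5%.

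**Step 4: the planned arms.** 200×5 = 1000, 150×6.7 = 1005 and 250×4 = 1000 patient-years per group. None reaches 1049 or 1065.

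**Step 5: other rows.** At one-sided 0.05 and margin 1.5%:

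| Test rate | Table 1 | Poisson score |
|---|---|---|
| 4.5% | 381 | 407 |
| 5.0% | 504 | 540 |
| 6.0% | 992 | 1065 |
| 7.3% | 3739 | 4040 |

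Over all 24 entries the Poisson score figure is 6.4% to 8.2% above the printed one.

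**Step 6: sensitivity to the SAP's own settings.**

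- *One-sided 0.025* (the non-inferiority side of a two-sided 0.05 test). The Poisson score requirement is 1354, against 1260 in Table 1. Power at 1000 is 67.2%; Table 1's binomial method gives 70.4% there.
- *Relative risk.* The documents give no ratio margin. If 1.5 points on 7.3% is read as a ratio of 8.8/7.3 (an assumption), the Wald log-ratio test at one-sided 0.05 needs about 1280 patient-years and has about 71% power at 1000.

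**The case against.** The strongest reply is that nothing is miscalculated. The protocol names the proportion test, and every entry is right for it. The SAP also defines the primary endpoints as binary (2.3.1) and compares percentages by chi-square or Fisher tests (9.1). The text says only around 1000 patient-years, the loss is about 2 points, and the choice between Wald and score forms moves the requirement by 16 patient-years. A true test rate of about 5.94% instead of 6.0% would restore 80% power at 1000 in the Wald form. Protocol III.B also lets follow-up run until exposure is sufficient, up to 8 years for a patient. The missing 65 patient-years are about 4 months each for 200 patients. Finally, 78% is not the power of the analysis in the SAP either.

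Most of this stands. The arithmetic is sound, the effect is small, and 78% needs its conditions stated. The binary-endpoint argument does not rescue the table. The chi-square, Fisher and Kaplan-Meier analyses take the patient as the unit, about 200 per group, and no analysis in the SAP treats 1000 patient-years as independent yes/no trials. The criterion that II.D sizes is the linearized rate.

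A reader might infer that Table 1 contains calculation errors, or that the trial is materially underpowered and must enrol more patients. The documents support neither: all 24 entries reproduce, and the shortfall from this source is about 2 points.

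**Conclusion.** The point holds as a small mismatch between the sizing model and the stated criterion. For a difference of two rates, 80% power needs about 1050 to 1065 patient-years per group (Wald to score) rather than 992. At 1000 the power is about 78%, a loss of roughly 1.5 to 2.2 points depending on the formula.

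This rests on the plan's own rates and margin, one-sided 0.05, a test of the rate difference, and events that are independent within patients. At those rates 78% is an upper figure. Repeat events clustered in the same patients would lower it, by an amount that the documents do not allow one to compute.

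It would also be wrong to read 78% as the power of the final analysis. SAP 6.5 sets two-sided 0.05 unless otherwise noted, and SAP 9.1 analyses linearized rates by relative risk with 95% confidence intervals. Those differences move power more than the variance model does, to about 67% for the significance level alone. They are separate questions, but any restated figure depends on how they are settled.

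**What to change.** 1. Recompute Table 1 for a difference of two Poisson rates, name the formula, and head the columns as rates per patient-year.
2. In Protocol II.D and SAP 4, either state power as at most about 78% at 1000 patient-years per group, or name about 1065 patient-years per group as the exposure for 80%.
3. Beside that figure, state its assumptions: rate-difference test, one-sided 0.05, no clustering of events within patients.
4. Reconcile it with SAP 6.5 and SAP 9.1. Say which significance level and which scale decide non-inferiority. If one-sided 0.025 applies, the figure to state is about 67% at 1000. If the ratio scale applies, a ratio margin must be given first.

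The cost of items 1 to 3 is a replacement table and a revised power statement in each document. No extra enrolment is needed if the power is restated. The downside is a slightly less favourable stated power.

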The primary study endpoints are the rates of occurrence of valve thrombosis, thromboembolism, all major and minor bleeding events whether or not related to drug therapy, reoperation, explant and death. Other valve related adverse events including endocarditis, hemolysis, hemolytic anemia, paravalvular leak and structural and non-structural dysfunction are secondary endpoints. All events shall be as defined by the AATS/STS guidelines ^[2] for reporting valve study results.

Effectiveness -

Effectiveness endpoints are also secondary endpoints and shall be New York Heart Association (NYHA) functional classification and the echocardiographic hemodynamic parameters of peak and mean gradient and effective orifice area (EOA). Echocardiographic exams shall also evaluate indexed EOA, performance index, cardiac output, cardiac index and amount and location of any valvular regurgitation.

B. Follow-up Regime and Intervals

The intent of the study design is to treat mechanical valve patients with less aggressive anticoagulation. The control group drug regimes are those from the recommendations for mechanical valves of the ACCP^[3] and the AHA/ACC^[4], while test group regimes are either a clopidogrel/aspirin mix for low risk aortic patients or reduced Coumadin to just below the present recommendations but with aspirin added. Patients will be maintained on Coumadin/aspirin beginning immediately postoperatively, with heparin used from operation until INR target is reached. Randomization and transfer to test group will occur at the 3-month visit. INR control will be accomplished using home monitoring with the system provided by QAS or in Italy with systems as provided within the processes used in medical care there. The patient in consultation with his/her physician will also make drug dosage adjustments.

Patients will be followed at 3 months, 6 months and 1-year, then annually thereafter until the study is completed when the patient groups reach sufficient patient-years experience at up to 8-years of follow-up for any individual patient and at least 1-year follow-up for all patients. Visits will be scheduled within 1-month of the appropriate anniversary. Follow-up will be conducted by physician visit.

C. Investigational Procedures

The sponsor will provide case report forms (CRFs) or equivalent electronic data management tools to each principal investigator for the purpose of recording patient data. Assessments will be obtained for the preoperative, operative and discharge period and postoperatively at three and six months and annually to 5 years from the date of implant (Table 2 summarizes the required information at each visit). A follow-up schedule will be provided for each patient based on the implant date.

This protocol is designed to be used within the normal daily practice of each center. No specific instructions other than those in the labeling are given on valve orientation or concomitant drug therapies. This will result in a study that defines complication rates under the various drug therapies.

The investigator will make every attempt to follow the patients and will document the information gathered during the follow-up visits on the CRFs. Follow-up

ata Record
Д
and
Progress
nt
iei
at
Ч
2
Ö
ple
Ta

visits should be made in person; telephone or questionnaire follow-up is not allowed. The patients will be encouraged by the investigator to report any address or telephone number changes. They will also be informed of the importance of returning for scheduled follow-up visits even if they are not having any problems. All dates within the study will be recorded as month/day/year using numeric designators for months. If additional space is needed on any form for any data, the data can be placed on a separate sheet and attached to the form.

The study coordinator should submit preoperative, operative and discharge case report forms within 30 days of the implant. As an exception, these CRFs may be forwarded within 30 days of discharge, if discharge is delayed by patient complication.

All appropriate sections of the CRFs must be filled out accurately and completely. All case reports form must be reviewed, signed and dated by the investigator. The CRFs should be sent expeditiously to the monitor, when completed, and be kept in the patient record notebooks or electronic files provided by the sponsor.

To protect patient confidentiality, the sponsor will use the information from the CRF's for statistical and device tracking purposes only and will treat medical records as confidential as required by United States law and regulation. For this reason, the sponsor is not routinely collecting patient names, but using a study number or initials, if necessary, for patient identification; thus better protecting patient confidentiality. A representative of the U.S. Food & Drug Administration or other appropriate regulatory authority may look at, and perhaps copy, some of the medical records; these organizations also have rules for protection of patient privacy that they must follow.

Enrollment Process and Options -

The following procedures may be used for enrolling patients into the study:

AVR High Risk and MVR Patients

- From review of patient charts determine the patient's eligibility for inclusion in either of these two groups.
- Patients that eventually qualify for high risk AVR based solely on hypercoagulability testing, which must be done preoperatively off warfarin, must be recruited preoperatively as described below under low risk AVR.
- All other patients can be approached for consent either preoperatively or postoperatively up to 60 days at the discretion of the investigative site. MVR patients may be enrolled up to 1 year postoperatively.
- Once a patient has consented initiate the patient in the Clinipace database by starting a preoperative form which will automatically assign the patient number for the study. Do not assign numbers manually.
- In North America then complete the home monitoring prescription paperwork and forward to QAS right away so the insurance qualification process can begin.
- In North America randomize the patient 2 weeks prior to their 3 month visit postoperative or for MVR patients at enrollment visit if greater than 3 months postoperative and provide QAS with the study INR target range for the patient

and the home test machine order. Use Italian home monitoring procedures elsewhere, and randomize as above.

• Conduct the 3 month visit which will start the study for the patient. Change drug therapy per the protocol and randomization result.

Low Risk AVR Patients (No longer active arm of trial)

Determine the patient's potential eligibility for the low risk AVR group understanding that the group may change to high risk AVR pending the results of the hypercoagulability and drug response testing described below.

Completely Preoperative Testing Option

- Approach all eligible patients for informed consent, and once consent is given, start the laboratory testing program. At this time also enter the patient into the Clinipace database for the assignment of the patient number.
- Order clopidogrel through Canada Drug or the local VA pharmacy as appropriate. This order is for 10 – 75mg tablets to be shipped to the patient's home overnight. The prescription should prescribe a 300 mg loading dose on day 1 and 75mg/day for 1 week. Instruct the patient to take the drug in this manner. Also instruct the patient to buy and take 325 mg aspirin once daily.
- Have the patient return for testing at least 5 days later. Confirm that they are taking their antiplatelet medications. Draw the appropriate blood samples per the Accumetrics and HRL instructions and also get the required urine sample. Process all the samples for HRL per the HRL instructions and the Accumetrics P2Y12 test within 4 hours. Regardless of the Accumetrics test result, freeze and ship all other samples per the HRL instructions. Clopidogrel can be stopped as soon as the P2Y12 test is successfully done. A P2Y12 result of <35% inhibition disqualifies the patient but the full testing should still be done. A urine thromboxane result of >298 pg/mg disqualifies the patient.
- Enter the shipment information into the Clinipace database and wait 24 hours for the lab to respond that the samples have arrived properly. Hint: arrange the testing and shipment schedule to occur early in the work week to avoid any overnight sample arriving at the lab on the weekend.
- If samples arrived in good condition, instruct the patient to stop taking the drugs and schedule the operation for at least 5 days later.
- Complete the home monitoring prescription paperwork and forward to QAS right away so the insurance qualification process can begin in case it is needed after randomization.
- Randomize the patient 2 weeks prior to their 3 month visit and either order clopidogrel for test group patients or provide QAS with the study INR target range for the control group patients and the home test machine order. The clopidogrel prescription is for a 90 day supply with 7 refills the dosing regime is 300mg loading dose on day 1 and 75mg/day thereafter.
- Conduct the 3 month visit which will start the study for the patient. Change drug therapy per the protocol and randomization result.

Preoperative Hypercoagulability and Postoperative Drug Response Option -

- Approach all eligible patients for informed consent, and once consent is given, start the laboratory testing program. At this time also enter the patient into the Clinipace database for the assignment of the patient number.
- Draw the appropriate hypercoagulability blood samples per the HRL instructions. The patient must be off warfarin for this testing. Process all the samples for HRL per their instructions.
- Enter the shipment information into the Clinipace database. Hint: arrange the shipment schedule to occur early in the work week to avoid any overnight sample arriving at the lab on the weekend, so keep any frozen samples until Monday if drawn on Friday for example.
- Complete the home monitoring prescription paperwork and forward to QAS right away so the insurance qualification process can begin in case it is needed after randomization.
- The patient's surgery can proceed under normal scheduling plans.
- At 50 days postoperatively, call the patient to determine that the patient's INR is stable and in target range then order clopidogrel through Canada Drug, or the local VA pharmacy as appropriate. This order is for 10 75mg tablets to be shipped to the patient's home overnight. The prescription should prescribe 75mg/day for 1 week to 10 days (no loading dose). Instruct the patient to take the drug in this manner. Also instruct the patient to buy and take 325mg aspirin daily. If the patient's INR is high adjust the Coumadin dose to bring the INR in range before starting clopidogrel. Also confirm that the patient is taking his/her antiplatelet medications. It is also recommended that a CBC be done locally to make certain that the patient is not clinically anemic, which could create an inaccurate P2Y12 measurement.
- At 60 days bring the patient into the office for their drug response testing. Draw the appropriate blood samples per the Accumetrics instructions and get the required urine sample for HRL. Process the blood sample for the Accumetrics P2Y12 test within 4 hours. Also freeze and ship the urine per the HRL instructions regardless of the P2Y12 result. A P2Y12 result of <35% inhibition disqualifies the patient but the full testing should still be done. A urine thromboxane result of >298 pg/mg disqualifies the patient.
- Enter the shipment information into the Clinipace database. In 24 hours the lab should respond that the sample has arrived properly. Hint: arrange the testing and shipment schedule to occur early in the work week to avoid any overnight sample arriving at the lab on the weekend.
- Randomize the patient 2 weeks prior to their 3 month visit and either order clopidogrel for test group patients or provide QAS with the study INR target range for the control group patients and the home test machine order. The clopidogrel prescription is for a 90 day supply with 7 refills the dosing regime is 300mg loading dose on day 1 and 75mg/day thereafter.

• Conduct the 3 month visit which will start the study for the patient. Change drug therapy per the protocol and randomization result.

Preoperative Procedures -

The investigator will determine and document on CRFs whether each patient meets the selection criteria previously outlined before enrollment into the study. He will also obtain informed consent for study participation from each patient prior to implantation of the study device. A copy of the informed consent form will be kept by the investigator in the patient's study notebook. Patients not meeting the selection criteria or not receiving informed consent **should not** be enrolled in the study.

The investigator will determine and record on CRF1 each patient's demographics and relevant medical history, i.e., age at implant, gender, New York Heart Association (NYHA) functional class, cardiac rhythm, disease etiology, previous cardiac surgery, relevant information to determine thromboembolic risk group and valve lesion (i.e., stenosis, regurgitation or mixed stenosis/regurgitation).

These instructions are made to assist the study coordinator in filling out the form. Complete all items on the form. If information is unavailable to answer any item, make a note on the form and attach an explanation, as appropriate. When asked to specify a particular answer, use a short description. Please check any and all items that apply to the patient.

For patient study number, use a 6 digit code. The first two digits are your center number, as assigned by the sponsor. The third number represents the position of the implant; 1 for aortics, and 2 for mitrals. The last three digits are assigned sequentially to each patient. For example, if your center number is 99, your first aortic patient study number is 991001, your first mitral patient study number is 992001, and so forth. Once the patient study number is assigned on CRF1, use of the patient study number is required to identify the patient on subsequent forms.

NYHA functional class uses the nomenclature of that association. For the purposes of this study the commonly used classes of IIa and IIb are not used, either subgroup is considered class II.

Any failure to obtain prior informed consent must be reported to the sponsor, and the institution within 5 working days.

Previous cardiovascular surgery should be noted with a one or two word name of surgery and the date performed (page 2 of CRF1). Room is given for three prior procedures. Attach a separate explanation if more prior surgery was done. For coronary artery bypass surgery, please note the number of grafts by the following notation: CABG x 2 = double graft; CABG x 3 = triple graft; and so on.

If the patient has been maintained on any permanent or long-term preoperative Coumadin therapy, the preoperative INR should be measured and recorded within 72 hours prior to surgery. **Operative Procedures** -

The surgical technique employed is that developed and perfected by the principal investigator in his normal practice of cardiac surgery. Operative details such as cardioplegia are not specified in the protocol, but must be documented on CRF2.

The investigator will record on CRF2 information regarding the particular valve(s) implanted and other details concerning the surgery such as suture technique and any concomitant procedures. Carefully record the valve position, size and serial number.

Use the patient study number assigned on the preoperative form (CRF1) to identify the patient. Check any and all of the items that apply to this patient. Where explanations are needed, print a brief description of the required data.

For concomitant procedures, there are spaces for these additional procedures. Write in the name of the procedure done. For coronary artery bypass grafting, also note the number of grafts (i.e., CABG x 2 = double graft, CABG x 3 = triple graft, and so on).

Where requested, attach additional CRFs or reports.

The Implant Registration Card is included with the valve packaging and is used for tracking valves within the study. It must be completed and returned to the sponsor within 24 hours of the surgery. Sending a copy of the card to the sponsor by facsimile or e-mail is adequate to fulfill this requirement.

There is also a permanent patient record card included in the package labeling. This card is to be completed and given to the patient as a form of permanent medical identification.

Early Postoperative/Discharge Procedures -

The investigator will record the date of the patient's discharge from the hospital and the date of the early follow-up examination on CRF3. The early follow-up exam records the patient's status at the time of discharge or at 30 days, whichever comes first. The patient's NYHA and cardiac rhythm status and any complications will be noted along with the patient's amticoagulation therapy. It is important to record the international normalized ratio (INR) at the time of the exam. Wherever possible this value should be within the therapeutic range required by this protocol in section II C.

At each postoperative assessment, the investigator will need to determine the patient's availability for future follow-up. If any patient needs to be seen at other than a regularly scheduled follow-up visit, the same follow-up information as required at regular times will be documented by the investigator on the follow-up form, and that follow-up will be indicated as an off schedule visit.

Late Follow-up Reporting -

Late follow-up is required in at 3 and 6 months postoperative intervals, and annually postoperatively through at least 1 but no more than 8 years. For MVR patients enrolled greater than 60 days postoperatively, follow-up will be at 3-months post enrollment then annually on the anniversary of implant. This is also done on CRF3. Follow-up must be in person; telephone or questionnaire follow-up is not allowed. If a patient misses a scheduled follow-up visit, the investigator must make an effort to contact the patient to determine the reason for the missed visit. A new visit should be scheduled, but if the patient refuses to return for follow-up or otherwise cannot be

contacted, the patient is then recorded as lost or withdrawn from the study. The efforts to maintain contact will be documented on the follow-up form, and every effort will be made to minimize the number of patients lost (zero being preferable). Thus, a follow-up form (CRF3) is due annually on each patient whether or not follow-up has occurred.

At the 3 month follow-up each patient shall be randomized into treatment group. The investigator will log into the data management system to be assigned the random (test or control) group for the patient per the web-based procedure briefly described below. If any patient has suffered a thrombotic or bleeding event during the initial 3 month period, he/she shall not be randomized into a group and shall be considered a screening failure and the event shall not be analyzed with any group under an intent-to-treat classification.

The randomization module implements a standard randomization algorithm, Marsenne Twister that is implemented in Java. (Matsumoto M. and Nishimura T., "Marsenne Twister: A 623-Dimensionally Equidistributed Uniform Pseudo-Random Number Generator", ACM Transactions on Modeling and Computer Simulation, 1998;8:3-30.) The patented randomization module can provide block and stratified randomization results.

The procedure automatically executes upon eligibility documentation for a study subject. The randomization result is presented on the screen instantaneously upon eligibility documentation using sponsor provided language and is also stored in the study database. The Tempo electronic randomization process ensures only eligible subjects are randomized and no errors are made in storing the correct result of randomization. The Tempo system audit trail documents the randomization results and time of execution.

Late follow-up information includes in all cases the patient initials or ID, cardiac rhythm, NYHA classification, and anticoagulant therapy information, including where applicable the most recent INR provided by the patient or QAS. For any new complication, the complication report (CRF4) must be completed and attached. All complications that have occurred between follow-up examinations must be reported on the form. Echocardiography per section III D is required at 1, 3 and 5 years.

Complication Reporting -

All complications should be recorded by the investigator on CRF4. Start and stop dates and etiology should be noted. The investigator will attempt to evaluate the relationship of all deaths, reoperations, explants, or cardiovascular complications to the study valve as presented in the AATS/STS guidelines ⁽²⁾ and will provide pertinent details of the event on CRF4. Copies of autopsy report and/or death summary must be included where applicable.

The investigator will report any serious or unexpected complication occurring during the investigation to the monitor within 24 hours, followed by a written report in ten working days, after the investigator first learns of the event. A serious or unexpected complication would include those complications not expected, or those occurring at a greater rate than expected when compared to the review requirements of this study (see section III F).

Adverse events are defined by the United States FDA as complications, meaning:

"Operative mortality, morbid events, and consequences of morbid events. Complications may or may not be device related."

This study uses the term "complication" to mean any adverse event or adverse device effect (a device-related adverse event), which may be mild, moderate, or severe. If as a result of a complication during a clinical investigation a subject has to be hospitalized, if hospitalization is unduly prolonged because of potential disability, if hospitalization is unduly prolonged because of potential danger to life, if a reoperative intervention has been necessary, or if the event is terminal, the complication is regarded as severe.

The definitions which appear in the following sections will be used to report complications associated with the use of the On-X prosthesis. Complications will be recorded and dated when they are observed or estimated to have occurred and treatment(s) documented. An event will be recorded once unless there are multiple occurrences of that event. For example, a cerebrovascular accident (CVA) reported once with sequelae still present at subsequent follow-visits will not be reported again. If another CVA occurs that is unrelated to the initial episode, then it is reported as a separate incident.

